RAI is generally well tolerated. Complications are rarely life-threatening but can negatively affect patients' quality of life. (Fard-Esfahani 2014) Side effects of I-131 occur in many areas and organs systems. They are most often categorized by time of occurrence after therapy. Early effects are those that begin immediately after therapy until around 10 days post-treatment. Intermediate effects occur during the remainder of the first year after therapy and late effects can be experienced any time during the long-term follow-up period. (Van Nostrand, 2009)

Within the head and neck, salivary gland dysfunction is the most frequently described complication after I-131 therapy. (Clement 2015) Usually salivary gland dysfunction occurs early and is transient, but it may also persist or appear late. Xerostomia, occurring in 2-55% of patients, is generally the result of radiation-induced sialoadenitis. (Van Nostrand) Obstruction of Stensen's and/or Wharton's duct due to inflammation also leads to pain and swelling and can ultimately result in ductal narrowing secondary to fibrosis. Ensuing hyposalivation can become chronic and leads to problems with oral hygiene, dental caries, and candidiasis.

Salivary glands concentrate iodide by a factor of 30-40 compared to blood and, as a result, the dose to salivary gland during first 12 hours after administration could be as high as 6Gy. (Fard-Esfahani 2014) Effect on salivary gland function is dose-related and more prominent in the parotid glands. Evaluation of volume in salivary glands using sonography shows significantly increased volume in the parotid glands after RAI dependent on received activity and time from irradiation. Occasionally radiation

sialoadenitis will result in facial nerve paralysis secondary to compression by a swollen parotid gland.

A review by Clement et al of 683 pts found that the prevalence of objective salivary gland dysfunction after I-131 ranged from 37-72%. In general, higher cumulative activities of I-131 are associated with increased risk of salivary gland dysfunction. Symptomatic salivary gland dysfunction correlated well with cumulative I-131 activity. (Clement 2015)

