6.0 STUDY PROCEDURES

6.1 Study Visit Schedule Screening: Trial Coordinator will screen the office charts for possible inclusion in the trial. Labs for the screening part will be available from pre-admission testing that is standard of care for initial biopsy. Women of childbearing potential (WOCBP) should have a pregnancy test done as part of pre-admission testing prior to surgery (within 14 days of study enrollment). If a test was not done, it will be done at time of consent.

Visit 1: Subjects who meet inclusion criteria after reviewing the initial biopsy, laboratory data, and clinical chart will be approached the day of their follow up after initial biopsy. The study coordinator will meet with the prospective candidates and go over the protocol, answer questions and obtain informed consent. If the subject is agreeable to the study, a physical exam will be performed, subject will be randomized and metformin or placebo will be dispensed. Instructions on how to take study drug will be given and times for follow up phone calls for tolerability and safety will be arranged with participants. Participants will be instructed to call with any side effects or adverse events that occur in the interim of the follow up phone calls.

The exact date to start the metformin will be determined this visit based on the planned date of radioactive iodine (RAI) administration. One week prior to the radioactive iodine treatment, the first dose of metformin can start. Metformin or placebo will be stopped the day before RAI treatment is received.

Per standard of care, a pregnancy test will be done within 72 hours of starting radioactive iodine administration.

Quality of life measures will be assessed prior to start of metformin.

Quality of life measures will be administered on an IPad through a website (https://az1.qualtrics.com/jfe1/preview/SV_57qgtgkjaexOy9f). Participants will be

identified only by study ID number. Paper questionnaires will be provided if the forms cannot be completed electronically.

Metformin or placebo administration will resume the day after the last treatment with radioactive iodine and will be taken until the end of bottle (2 weeks after RAI treatment).

Visit 2: At the first visit following completion of metformin administration for two weeks after RAI, patients will be approached for bottle and pill reconciliation, review of compliance with appropriate lab draws, as well as follow up of side effects and adverse events.

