Appendix A: Schedule of Events

Appendix A: Schedule of Events

Study Procedures	Screening	Visit 1	Visit 2 (End of Treatment) ^E	Follow-up ^F
Informed consent		X		
Inclusion/Exclusion Criteria	X	X		
Demographics, Medical history	X	X		
Physical examination, vitals, weight, blood pressure		X	X	
Randomization		X		
Quality of Life Questionnaires ^D		X	X	X ^C
Pathology Report histologic confirmation of disease if available	X			
Concomitant meds	X	X		
Toxicity and AE Assessment		X	X	X ^I
Pregnancy test ^J	X	X		

Treatment/ Intervention				
Metformin ^G		X	X	
Placebo ^H		X	X	
Radiation Treatment		X	X	
Correlative Studies				
Blood sample collection ^A		X	X	X ^C
Saliva sample collection ^B		X	X	X ^C

- A. Two 7ml purple top tubes are to be drawn at each time point and transported directly to [name] laboratory.
- B. 5ml of saliva is to be collected at each time point and transported directly to [name] laboratory.
- C. Blood samples, saliva samples, and quality of life questionnaires will be collected every 3 months for the first year post treatment. Collection will occur at participant's regularly scheduled appointments.
- D. Quality of life surveys include: EORTC QLQ – H&N35, modified Vanderbilt Head and Neck Cancer Symposium Survey, University of Washington Quality of Life Questionnaire, and Xerostomia Questionnaire (XQ). All questionnaires will be administered online via an IPad provided at the visit.
- E. Visit will occur following completion of metformin treatment for 2 weeks after RAI
- F. Patients will be seen at regularly scheduled appointments every 3 months for the 1st year post treatment. Participant's medical records will be reviewed every 3 months for 24 months
- G. The initial starting dose of metformin will be 500mg orally daily for 3 days which then will be increased to 500mg twice daily and, if tolerated, further increased to 1000mg twice daily after day 6. Patients will maintain 1000mg twice daily dosing until 2 weeks after completion of radiation. If patient must have CT scan with intravenous contrast, metformin will be held and participant will be instructed to start metformin the day following the scan.
- H. Placebo will be given as 500mg tablets twice daily with no dose escalation.
- I. Assessment for AEs will occur as a phone call performed 2 weeks after the last dose of metformin.

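### No symptom questionnaire is named between the pre-drug baseline and Visit 2, about two weeks after RAI, so early symptoms that clear before then are not measured

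*Combined protocol and SAP*

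**What the plan says.** The secondary objective (1.1, 2.2) is the effect of metformin on xerostomia, xerophthalmia and dysgeusia, measured by four questionnaires. It is not restricted to persistent symptoms.

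- **Course of symptoms.** Section 1.2 says of the salivary glands: "Usually salivary gland dysfunction occurs early and is transient, but it may also persist or appear late". It classifies side effects by time of occurrence: "Early effects are those that begin immediately after therapy until around 10 days post-treatment".
- **Baseline.** Section 6.1: "Quality of life measures will be assessed prior to start of metformin". On drug start it says: "One week prior to the radioactive iodine treatment, the first dose of metformin can start".
- **Visit 2.** Section 6.1 places it thus: "At the first visit following completion of metformin administration for two weeks after RAI". Footnote E of Appendix A agrees: "Visit will occur following completion of metformin treatment for 2 weeks after RAI". Section 5.6 puts the same visit at roughly two weeks after RAI. No visit window is given.
- **Questionnaires after baseline.** Appendix A marks them at Visit 2 and at follow-up every three months in the first year. It has no column between Visits 1 and 2. The Visit 2 paragraph in 6.1 does not mention them: "patients will be approached for bottle and pill reconciliation, review of compliance with appropriate lab draws, as well as follow up of side effects".
- **Other contacts around RAI.** Section 2.1 has samples taken by day 3 after RAI, and 6.4.1 has exosome samples collected in person. Sections 1.4 and 5.3 plan tolerability calls at each dose escalation and weekly afterwards. None of these names a questionnaire. Section 3.1 says, without dates, that surveys are completed at every postoperative visit.

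**The concern.** By the protocol's own account, salivary dysfunction is the most often described head and neck complication of I-131 and usually comes early and passes. The schedule measures symptoms before drug start and then not until the post-RAI drug course is over. Patients take study drug from day +1 to day +14 after RAI, so the period in which early symptoms arise while on drug has no questionnaire in it.

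The objective covers RAI-induced symptoms in general, while the data would cover those still present about two weeks after RAI or appearing later. With at most 16 patients per arm, a finding of no difference could not be told apart from a failure to measure when symptoms were present. That matters for a pilot whose use is to inform a later trial.

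**Working it through.** RAI is day 0.

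**1. Date of Visit 2 (the plan's figure: roughly two weeks after RAI, 5.6).**
- Metformin bottle: 69 tablets (5.10.3). The first six days use 3 x 1 + 3 x 2 = 9. The rest last (69 - 9)/4 = 15 days. Total 3 + 3 + 15 = 21 dosing days.
- Placebo bottle: 42 capsules at two a day (5.11), 42/2 = 21 dosing days.
- Drug starts at day -7 and is not taken on the day of RAI, so days -7 to -1 use 7 dosing days. The other 21 - 7 = 14 run from day +1 to day +14.

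Both bottles end on day +14, which reproduces the two-week figure. The earliest Visit 2 is about day +14 or +15.

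**2. Shortest interval without a questionnaire.** The latest possible baseline is day -7. The interval is 14 + 7 = 21 days, or 15 + 7 = 22. It is longer if baseline is taken earlier or Visit 2 slips.

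**3. Position of the early period.** Early effects begin between day 0 and about day 10, wholly inside the interval. That period closes 14 - 10 = 4 days (or 15 - 10 = 5) before the earliest Visit 2. Questionnaires named in it: none.

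**4. What is missed.** A symptom with onset on day d is over before a visit on day V if it lasts less than V - d days. With V = 14:
- onset on day 1: missed if shorter than 14 - 1 = 13 days
- onset on day 10: missed if shorter than 14 - 10 = 4 days

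Longer-lasting symptoms are still present at Visit 2 and are captured, as are late ones. The rule assumes that no recall period reaches back; the documents state none.

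**5. Number of patients.** Group size: 14/(1 - 0.10) = 15.6, rounded up to 16 per arm, as in 7.1. Section 1.2 gives xerostomia in 2-55% of patients: 0.02 x 16 = 0.3 to 0.55 x 16 = 8.8 per arm. The share that clears before Visit 2 is not given and could be anything from none to all. The number missed per arm therefore lies between 0 and 8.8, and the documents do not narrow it. For taste they give neither a frequency nor a time course.

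**6. Most generous reading of 3.1.** If a survey accompanies the sample taken by day 3, the uncovered stretch shrinks to about day 3 to day 14, or 14 - 3 = 11 days. Symptoms that begin after day 3 and clear before Visit 2 are still missed.

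**The case against.** Several points on the other side stand.

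- **Onset is not duration.** The ten days in 1.2 say when early effects begin. A reader might infer that they are over by day 10 and that Visit 2 misses them all. The text does not say so, and it also allows for symptoms that persist or come late. The loss is partial.
- **A survey by day 3 is a possible reading.** Section 3.1, taken with 2.1 and 6.4.1, could imply one, so it would be too strong to say that no contact falls in the two weeks after RAI. But Appendix A shows no such survey, and most of the interval would remain open.
- **Visit 2 is not open-ended.** From the Visit 2 paragraph in 6.1 a reader might infer that the visit can fall at any later time, or that the first post-RAI questionnaire comes only at three months. Section 5.6 dates the visit and Appendix A marks the questionnaires there. The 6.1 list also leaves out the physical examination and the blood and saliva samples that Appendix A marks, so it is abbreviated. It needs aligning; it does not cancel the Visit 2 questionnaire.
- **Other channels exist.** Weekly calls and adverse event questioning (8.2) may record dry mouth or taste change, but they do not yield scores on the named instruments.
- **The stakes are limited.** These are secondary outcomes, described in the Study Summary as mainly descriptive, in a 32-patient pilot.

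**Conclusion.** The point holds as a gap in coverage. On the operative schedule no questionnaire is named for at least 21 days around RAI, and that interval includes the whole period in which the protocol expects early effects to start. The questionnaire comparison of dry mouth and taste cannot detect an effect of metformin on symptoms that arise and clear before Visit 2. It can detect effects on symptoms still present then, and on persistent or late ones.

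A reader might infer that the comparison is biased towards no difference. The documents do not support this. A later assessment estimates the effect at a later time, which is a narrower target than the stated objective but not a biased estimate of it. Nor do they say that a metformin effect would be greatest in the first two weeks.

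The conclusion assumes one RAI administration on day 0, dosing as labelled and no recall period reaching back before Visit 2. Its size in patients cannot be derived. For taste it is weaker, because only the salivary time course is described. The primary CBC analysis and the sample size are untouched. This is a cheap and worthwhile improvement to a secondary outcome.

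**What to change.** 1. Add one administration of the Xerostomia Questionnaire and the taste measure already in the set at about day 7-10 after RAI, for both arms, counted from RAI and not from dose escalation (the placebo arm has none). Use the existing web form or paper.
2. Time it with a planned weekly call and use that call only as a reminder. The patient should complete the form alone, because study staff are not blinded (5.9).
3. Footnote D of Appendix A has the forms completed on a tablet at the visit. Amend it to allow remote completion.
4. Align 3.1, 6.1 and Appendix A: list the questionnaires among the Visit 2 tasks in 6.1, give Visit 2 a window counted from RAI, and say whether 3.1 intends a survey with the sample taken by day 3.
5. State each instrument's recall period. Report early (day 7-10) and persistent (3 to 12 month) symptoms separately, adding the early time point to the models for these outcomes in 7.2.

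Cost: protocol wording, one short extra form for each of 32 patients, and a small change in how the form is delivered. The downside is minor patient burden. Treatment, sample size and the primary analysis do not change.

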6.3 Dose Delays and Dose Modifications

Please see Section 5.3.

6.4 Laboratory Procedures/Evaluations

6.4.1 Clinical Laboratory Evaluations

To assess changes in CBC, patients will be provided prescriptions for lab draws to be performed at previously specified time intervals and instructed to have their results forwarded to the Department of Otolaryngology. To assess the effects of metformin on serum and salivary exosome profiles, samples will be collected in person by office nursing staff at follow-up visits to the Department of Otolaryngology and transported directly to [name] lab.

6.4.2 Special Assays or Procedures

Exosome profiles of serum and saliva samples will be isolated and analyzed in the laboratories of Drs. [name] and [name] using previously established protocols.

6.4.3 Specimen Preparation, Handling, and Storage

Blood and saliva will be collected in the Department of Otolaryngology, de-identified and analyzed in the labs of [name] and [name].

7.0 STATISTICAL PLAN

7.1 Sample Size Determination

The sample size was chosen to have adequate precision for estimating the effect size comparing groups with respect to change from pre-resection to post-resection. From data in Bikas et al, we estimate that the standardized effect size for comparing change from pre-resection to post-resection between groups will be at least 0.78 standard deviations. For a 95% confidence interval to have half-width of 0.78 SDs, 14 patients per group are required. Allowing for 10% attrition, we will recruit and randomize 32 patients (16 per group).

7.2 Statistical Methods

The primary objective of the study is to estimate the impact of metformin on change in complete blood count. Longitudinal measures of CBC will be modeled using mixed effects linear regression. Outcomes will be transformed as necessary (e.g., log transformed) prior to analysis. Fixed effects will include time (Pre-resection, Post-resection, 3 months post-resection, 6 months post-resection, 12 months post-resection), treatment (metformin vs. control) and treatment by time interaction. We will use a linear contrast to test the null hypothesis that change from pre-resection to post-resection is the same in the control and metformin groups. Secondary analyses will compare groups with respect to change from pre-resection to each of the follow-up times. Components of complete blood count will be analyzed with similar models.

Other longitudinally measured continuous outcomes will be modeled using mixed effects linear regression and longitudinally measured binomial and ordinal outcomes will be modeled using generalized linear mixed effects regression.

7.3 Subject Population(s) for Analysis:

All randomized participants with any data will be included in the analysis as randomized. Missing outcome data will not be imputed.

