2.0 STUDY OBJECTIVES

1. To estimate the capacity of metformin to mitigate radioactive iodine therapy-induced myelosuppression as assessed by CBC
2. To assess the capacity of metformin to mitigate known side effects of radioactive iodine therapy including xerostomia, xerophthalmia, and dysgeusia as assessed by standardized questionnaire
3. To analyze changes in serum and salivary exosome profiles following a trial of metformin administration in patients receiving radioactive iodine treatment

2.1 Primary Objective:

We have chosen complete blood count (CBC) as our primary endpoint and serum and salivary exosome profiles as secondary endpoints. To evaluate if treatment with metformin inhibits RAI-induced myelosuppression and induces faster recovery of white blood cell count to baseline values, the blood counts will be compared in the pre- and post-treatment samples. Blood parameters will include hemoglobin, red blood-cell count, white blood-cell count, absolute neutrophil count, absolute lymphocyte count, and

Thomas
Jefferson
University

platelet count. Blood and salivary samples will be drawn before surgery, before and immediately after treatment with metformin and RAI, and every three months thereafter for one year.

All blood samples will be taken by a phlebotomist or trained personnel. A baseline blood sample, consisting of two tubes of 1 cc of whole blood each, will be drawn before thyroidectomy as part of standard procedure at patients' pre-operative testing appointment. Patients will recover for a period of 6-8 weeks and identical samples will be drawn within 72 hours of starting metformin. Then samples will be drawn within three days before and within three days after RAI treatment, at the conclusion of metformin treatment, and every three months thereafter for one year. Blood parameters will include hemoglobin, red blood-cell count (RBC), white blood-cell count (WBC), absolute neutrophil count (ANC), absolute lymphocyte count (ALC), and platelet count. Assays will also be conducted on samples to assess metformin-induced changes in serum and salivary cytokines and growth factors, erythrocyte sedimentation rate (ESR), exosome evaluation, and metabolomics profile. 5 cc samples of patient saliva will be collected in specimen cups.

2.2 Secondary Objective:

- Assess safety and tolerability of metformin treatment in subjects undergoing RAI treatment for differentiated thyroid cancer

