3.0 STUDY DESIGN

3.1 General Design

Type of trial: Pilot Efficacy trial

Planned accrual period: 48 months

Planned follow-up period: 12 months

Planned enrollment: Total of 32 patients

Schema of the trial design, procedures, and stages:

Patients with a diagnosis of well-differentiated thyroid cancer who have undergone tumor resection and have indications for RAI treatment that meet our inclusion and exclusion criteria will be offered participation in this clinical trial. Patients who present to TJUH with a known diagnosis of differentiated thyroid cancer who plan to undergo surgical resection followed by radioactive iodine will be offered enrollment in the trial at the time of surgical scheduling. Patients who undergo lobectomy for atypia of undetermined significance/follicular lesion of undetermined significance or follicular neoplasm/suspicious for follicular neoplasm who are subsequently found to a malignancy will be offered enrollment at their first follow-up visit. After informed consent is signed and study subjects are randomized 1:1 to take metformin or placebo, patients will be administered metformin with dose escalation as tolerated until time of RAI treatment. There is no dose escalation for patients randomized to the placebo arm. Pre-operative and pre-RAI treatment CBC with differential will be compared to post-RAI treatment lab values. Standardized surveys assessing symptoms of xerostomia, sialadenitis, xerophthalmia and dysgeusia will be completed.

Participants' Follow-up: Participants' will have blood and saliva samples drawn post-op before metformin administration, before and immediately following RAI treatment, after metformin, and then every three months for 12 months. They will complete surveys at each post-op visit, and their medical records will be reviewed every 3 months for 12 months to assess for symptoms of myelosuppression, xerostomia, xerophthalmia, and dysgeusia. This will allow us to assess the radioprotective effects of metformin post-RAI treatment.

Purpose of the study: To estimate the radioprotective effect of metformin in subjects with differentiated thyroid cancer by evaluating both the ability of metformin to mitigate known side effects of radioactive iodine therapy as well as alter the exosome profile in the serum.

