4.0 SUBJECT SELECTION AND WITHDRAWAL

4.1 Inclusion Criteria

1. Diagnosis: Subjects with a diagnosis of differentiated thyroid cancer who have undergone total or near-total thyroidectomy and are candidates for I-131 treatment at TJUH are eligible to participate.
2. Age: Subjects must be ≥ 18 years of age and ≤ 90 years old.
3. Disease Status: Subjects must be diagnosed with differentiated thyroid cancer
4. Prior Therapy: Patients must have previously undergone or plan to undergo thyroidectomy. For those patients who have previously undergone surgery, pre-operative labs, including complete blood cell count with differential must be available.
5. Patients who have a negative urine pregnancy test prior to enrollment. This should be done as part of pre-admission testing prior to surgery (within 14 days of study enrollment).
6. Informed Consent: All subjects must be able to comprehend and sign a written informed consent document.

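### Section 7.2 leaves the arms' pre-resection means free to differ; a common-baseline model with unstructured covariance would probably narrow the primary interval at little cost

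*Combined protocol and SAP*

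**What the plan says.** Section 7.2 plans a mixed effects linear regression of the longitudinal counts. Time has five levels (pre-resection, post-resection, and 3, 6 and 12 months), and the remaining fixed effects are "treatment (metformin vs. control) and treatment by time interaction". The primary test is a linear contrast comparing the arms on change from pre-resection to post-resection. Section 7.2 adds that "Components of complete blood count will be analyzed with similar models". It names no covariance structure and no degrees-of-freedom method, and does not adjust for or constrain the baseline.

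Section 7.1 sizes the trial on precision alone: "For a 95% confidence interval to have half-width of 0.78 SDs, 14 patients per group are required". It then allows 10% attrition and randomises 16 per group.

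The baseline count is available by design. Section 2.1 states: "A baseline blood sample, consisting of two tubes of 1 cc of whole blood each, will be drawn before thyroidectomy". For patients already operated on, section 4.1 requires that "pre-operative labs, including complete blood cell count with differential must be available". Allocation is 1:1 by random permuted blocks (section 5.4), and study drug starts one week before RAI (section 6.1).

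**The concern.** Pre-resection is an outcome level and treatment has both a main effect and an interaction with time, so the model estimates a separate pre-resection mean in each arm. The primary contrast subtracts the whole observed baseline difference between arms. Under randomisation that difference is chance: the count precedes thyroidectomy, and no study drug is taken until after surgical recovery. Setting the two baseline means equal removes a parameter known to be zero in expectation, and the data then decide how much of the chance imbalance to subtract.

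Interval width is the trial's only sizing criterion, and 14 evaluable patients per group is few. At stake is precision that could be had from samples already planned.

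**Working it through.** **Inputs.** From section 7.1: two-sided 95% interval, n = 14 per group, half-width 0.78 SD of change. Not in the documents, so assumed over ranges: the pre-post correlation ρ and the post/pre SD ratio k.

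**1. The plan's own figure.** Half-width = t(0.975, 2n−2) × √(2/n).
- n = 14: 2.056 × √(2/14) = 0.777 SD.
- n = 13: 0.810 SD.

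So 14 is the smallest n meeting 0.78, and 14/0.9 = 15.6 rounds up to 16 per group. Section 7.1 reproduces.

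**2. Variances, covariance known.**
- Planned change contrast: (2/n) × SD_pre² × (1 + k² − 2ρk).
- Common-baseline contrast: (2/n) × SD_pre² × k²(1 − ρ²).
- Planned minus constrained: (2/n) × SD_pre² × (1 − ρk)², which is never negative and is zero when ρk = 1.

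With k = 1 the ratio of widths is √((1 + ρ)/2).

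**3. Cost of estimating the baseline slope.** With N = 28: √(1 + 1/(N−4)) × t(0.975, 25)/t(0.975, 26) = 1.0206 × 1.002 = 1.023. Simulated mean widths gave 1.022. Only this factor can widen the interval, hence the bound of about 2%.

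**4. Net result, k = 1** (step 2 ratio × step 3 factor, with 40,000 simulated two-visit trials per setting):

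| ρ | Formula | Simulated ratio | Change in half-width |
|---|---|---|---|
| 0.3 | 0.806 × 1.023 = 0.824 | 0.824 | −18% |
| 0.5 | 0.866 × 1.023 = 0.886 | 0.885 | −11.5% |
| 0.8 | 0.949 × 1.023 = 0.970 | 0.969 | −3% |
| 0.95 | 0.987 × 1.023 = 1.010 | 1.009 | +1% |

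Coverage was 0.948 to 0.951 for both methods. The simulated interval is the ANCOVA interval. In 2,000 complete five-visit trials the constrained maximum-likelihood estimate with unstructured covariance equalled the ANCOVA estimate (largest difference below 1e-15).

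To match the constrained model, the planned contrast would need about 20, 17.5 and 14.8 patients per group at ρ = 0.3, 0.5 and 0.8. These solve t(0.975, 2m−2) × √(2/m) = 0.777 × the simulated ratio.

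**5. Unequal SDs, unstructured covariance.**
- k = 0.8: −23%, −19% and −18% at ρ = 0.5, 0.7 and 0.8.
- k = 1.2: −5%, +0.5% and +2% at the same ρ.
- k = 1.25, ρ = 0.8: ρk = 1, so there is no gain and only the cost of about 2% remains.

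**6. The same constraint under a random intercept alone.** Five visits, ρ = 0.8, post SD 1.2 to 1.3 times the pre SD. The constrained estimate's true standard error was about 3.5% to 6% larger than the planned contrast's, yet its reported interval was about 6% narrower. Coverage was about 0.89 to 0.94. The ANCOVA interval in the same settings kept coverage of 0.949 to 0.954 with about 2% widening.

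**The case against.** **It is not a defect.** The change contrast is standard, unbiased under randomisation, consistent with a sample size based on change, and meets its target. This stands. A reader might infer that section 7.2 is wrong or that the trial misses its precision goal; step 1 shows otherwise. It does not remove the available gain.

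**The cost depends on the covariance.** Section 7.2 names no structure, and a random intercept is a natural default. A reader might infer that constraining the baseline costs at most 2% under any structure. Step 6 shows that it does not: the interval can be falsely narrow, and Kenward-Roger does not repair a misspecified covariance. The planned contrast is not immune either. With only the primary post visit at 1.3 times the pre SD, its random-intercept coverage was 0.917 in one check, against 0.879 for the constrained estimate. This objection stands and shapes the fix.

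**The gain cannot be fixed in advance.** Without ρ or SDs, a reader might quote the largest reduction as the expected one. The documents do not support any single figure, and the components of the blood count may differ.

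**Complete data.** The figures assume it, while section 7.1 expects 10% attrition. This stands as a limit on the sizes, not on the validity of the constraint.

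**The post-resection draw is not identified.** Section 2.1 says that "identical samples will be drawn within 72 hours of starting metformin", then that "samples will be drawn within three days before and within three days after RAI treatment, at the conclusion of metformin treatment". Section 3.1 likewise lists "blood and saliva samples drawn post-op before metformin administration, before and immediately following RAI treatment, after metformin". So there are four post-operative draws before month 3, the first before drug. A reader might infer that this undoes the proposal. It does not: the common pre-resection mean holds whichever draw is compared. Naming the draw is a separate point, though ρ and the size of the gain depend on it.

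**Conclusion.** The point holds as a cheap improvement. The planned contrast is valid but ignores a constraint that randomisation and sample timing justify.

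Under unstructured covariance with 14 complete patients per group and equal SDs, the expected half-width falls by about 18% at ρ = 0.3, 11.5% at 0.5 and 3% at 0.8, and rises by about 1% at 0.95. A smaller post-treatment SD increases the gain and a larger one can remove it. The expected loss is at most about 2%, reached when ρ times the SD ratio is near 1. That bound is conditional on visit-specific variances and correlations. ρ and the SD ratio are assumptions throughout.

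**What to change.** In section 7.2, pre-specify as primary a constrained longitudinal model with:
- the planned visits and one common pre-resection mean across arms;
- treatment effects only at post-baseline times;
- an unstructured covariance with visit-specific variances and correlations, not a random intercept alone;
- Kenward-Roger degrees of freedom.

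If it does not converge, use ANCOVA of the primary post-baseline count on the pre-resection count. Convergence is a real question, since five visits need 15 covariance parameters (5 × 6/2) from about 28 patients. Report the resulting difference with its 95% interval, keep the planned unconstrained contrast as a sensitivity analysis, and use the same form for each blood count component.

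The cost is a few sentences and a small change to the model code, with no new patients, samples or covariates. The constrained model keeps section 7.3's inclusion of everyone with any data; the ANCOVA fallback would drop patients lacking either count, and the plan should say so. The choice must be made before outcome data are seen, because picking the model afterwards would undermine the interval.
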